10.5 Sample Size

Power analysis: Estimated ITT 30-day cessation rates after 8-weeks of use for CKT and QG are based on published reports: CKT 26.2%, QG 8.3%. A power analysis for logistic regression using g*Power 3.1 software was conducted with the following parameters: 85% power to detect a group difference with $\alpha=0.05$ two-sided significance level, and estimated Group 1 proportion, p_1 , of 0.262 and a Group 2 proportion, p_2 , of 0.083. A sample size of 78 subjects in each group will yield 85% power to detect such a difference. To obtain this sample size, we plan to obtain consent from 195 subjects and enroll 156 into the study by downloading the assigned app, which reflects a conservative approach to the retention rate observed in our pilot data.

Data and Safety Monitoring Plan

“Clinical trial of an innovative digital therapeutic for smoking cessation with biochemical verification” (NIH Grant#: 1 R43 DA045395-01)

PI: [name].

Medical Monitor: [name]., Ph.D.

Summary of the protocol

The purpose of this SBIR Phase 1 project is to demonstrate the efficacy of Clickotine (CKT) in producing long-term cigarette abstinence in a value-based care population served by Click Therapeutics, Inc.’s commercial partner Magellan Behavioral Health, and to demonstrate the ability to base reimbursement from CKT on remote biochemical verification of successful cigarette abstinence. To do so, this SBIR Phase 1 project will support a pilot blinded, randomized, controlled trial of CKT versus the NCI QuitGuide (QG) app to test the hypothesis that CKT will produce greater 30-day abstinence rates than QG after 8 weeks of use. To demonstrate the feasibility of evaluating CKT in a Magellan value-based care population, half the study sample will be recruited from a Magellan value-based care population. To demonstrate the ability to base reimbursement on remote biochemical verification of successful cigarette abstinence, concordance rates between self-reported cessation on the outcome survey and the exhaled CO monitor result will be investigated; video monitoring of a subset of the first 50 study completers (first 25 completers in both CKT and QG groups) submitting the exhaled CO assessment will be conducted to validate the remote CO monitoring process. Smokers that are currently using a pharmacotherapy or Nicotine Replacement Therapy (NRT, including e-cigarette use) at study enrollment will not be eligible to participate. However, since some users are expected to choose to begin using smoking cessation pharmacotherapy or NRT during their quit attempt, users will be permitted to begin using smoking cessation pharmacotherapy or NRT during the trial if they so choose. Secondary analysis of the subgroup of NRT/pharmacotherapy users will be conducted to compare cessation rates between the CKT+NRT group and the CKT-only group, to address expected med/NRT use during the trial and to confirm the initial trial result that CKT+NRT is not superior to CKT-alone.

Half of the potential subjects will be recruited via social media advertising, while the other half will be recruited via mail to individuals covered by Magellan’s value-based care program. Both advertisements will seek smokers who are ready to set a quit date in the next 30 days with assistance from a study comparing smartphone apps that may help them quit. In a fully-remote study design, a pre-screening phone call for advertisement respondents will be conducted to assess eligibility and answer participant questions prior to obtaining informed consent. Informed consent will be obtained from participants via a web portal provided after the pre-screening call, and baseline demographic and smoking characteristic data will be collected via an online survey. Participants are then randomly assigned to download either CKT or QG. All participants who complete the initial survey and are enrolled into the study will be mailed a mobile CO monitor, the iCO+ Smokerlyzer (coVita, Santa Barbara, CA), with instructions on how to install its linked smartphone app and set the study email as the address to which CO results are to be sent. A final

online follow-up survey will be administered eight weeks after initial enrollment. A \$50 Amazon gift certificate will be provided in return for completing the online survey. The post-intervention survey will instruct subjects to obtain a CO reading with the iCO Smokerlyzer, to be transmitted to the study coordinator.

Primary outcome measure: self-reported 30-day abstinence from smoking on the outcome survey. Secondary outcome measures: iCO Smokerlyzer exhaled CO reading to confirm cigarette abstinence and assess concordance with self-reported abstinence; self-reported smoking cessation pharmacotherapy or nicotine replacement therapy (NRT) use.

Primary outcome data, including covariates to be included in regression analyses, are acquired via the web-based baseline survey and outcome survey. Data are conveyed via an automated process from the web-based survey into a format matching the study database. Research coordinator is responsible for entering the survey data into the study database within 72 hours of survey completion.

Secondary outcome data: 1) CO readings are automatically conveyed via email by the iCO Smokerlyzer App to the study coordinator, who will enter the result into the database (a numerical value in parts-per-million (ppm; <8 ppm is defined as evidence of cigarette abstinence); 2) self-reported NRT and smoking cessation pharmacotherapy use (including e-cigarette use) will be acquired via the outcome survey.

Data Analysis Plan:

[name], will conduct all study analyses after the study database is locked. All analyses will be performed on the intent-to-treat (ITT) population, with non-response imputed as continued smoking. 30-day smoking cessation status (dichotomous variable: yes/no) will be compared between the CKT and QuitGuide groups utilizing logistic regression. Two-sided p-values will be calculated from logistic regression models, with adjustments to the models by: race, education, nicotine dependence, and living with a partner who smokes, consistent with previous studies' models.

Concordance rates between self-reported 30-day abstinence and the remote CO monitoring result will be estimated, with concordance > 85% considered evidence of a valid reporting process by Magellan Behavioral Health. Concordance rates between the video-monitored and unmonitored groups will be compared to determine the value of video monitoring the CO assessment.

Secondary analysis of the subgroup of NRT/pharmacotherapy users will be conducted to compare cessation rates between the CKT+NRT group and the CKT-only group, to confirm the initial trial result that CKT+NRT is not superior to CKT-alone.

Quality Assurance

This fully-remote study will rely on digital procedures for data collection (e.g., web-based surveys; auto-emailed results of the CO assessment). Use of web-based surveys for primary data collection enables us to ensure the completion of data collected (forms can not be submitted unless complete and incomplete fields can be highlighted for participants). Survey data are conveyed in a format matching the study database for ease of entry into the study database by the research coordinator. The research coordinator will be responsible for entering all survey data into the study database within 72 hours of survey completion. Using these remote, digital procedures nature of the study results in data collection procedures that ensure the integrity of data collected. Validity of self-reported smoking cessation has been established in previous trials. To ensure the validity of the remote CO monitoring, a subsample of the first 50 study completers will be invited to complete the CO monitoring assessment on a live video feed to confirm identity.

Regulatory Issues

All Adverse Events that occur during study participation will be solicited from study participants in both groups via an email-based system for reporting AE/SAEs. Participants are made aware of the email system during the informed consent and study enrollment process. Reports are reviewed by the research coordinator and the PI within 24 hours of the report, and conveyed to the Medical Monitor (MM) for review and follow-up if appropriate. A Medical Monitoring form is completed for each AE reported to the MM, to include: a description of the event; onset/offset dates; treatment required and/or condition resolution; designation as AE/SAE; and judgment of association with study intervention. Expedited review will occur for all events reported by study participants that meet the FDA definition of Serious Adverse Events (SAEs) – i.e., any fatal event, immediately life-threatening event, permanently or substantially disabling event, event requiring or prolonging inpatient hospitalization, or any congenital anomaly. This also includes any event that a study investigator judges to impose a significant hazard, contraindication, side effect, or precaution. Reporting to NIH will be done according to NIH regulations governing SAE reporting: the PI will contact NIDA within 72 hours after the detection of a SAE. Reporting of Suspected Unexpected Serious Adverse Reactions (SUSARs; defined by WIRB as "unanticipated adverse device effects") to Western IRB will be done within 5 days of the SUSAR report in accordance with WIRB policy.

The PI will seek NIDA prior approval for any significant changes proposed to the protocol. All Western IRB actions relevant to the study, including changes or amendments to the study protocol, will be communicated to NIDA.

Study Stopping Rule: If at any time during the course of the study, the DSMB judges that risk to subjects outweighs the potential benefits, the DSMB shall have the discretion and responsibility to recommend that the study be terminated.

Disclosure of any conflict of interest in the DSM: There is currently no conflict to disclose in the DSMB membership. As noted below, the DSMB membership includes consultants with expertise in statistics, clinical trials and smoking cessation, who have been named on the grant as

consultants for these roles. These consultants are not employees of the sponsor nor do they have a financial interest in the outcome of the study. They will be compensated for their time consulting on the design and execution of the trial, including time spent serving on the DSMB.

Trial Safety

Potential risks and benefits for participants: The potential benefit of study participation includes successful smoking cessation. Although documented risks of smoking cessation apps have rarely if ever been demonstrated, potential risks may be considered minimal and no greater than those associated with standard of care behavioral therapies for smoking cessation. In this context, the benefit-risk balance for study participation is considered highly favorable. Furthermore, this trial will ascertain potential adverse events via medical monitoring procedures and will be conducted in compliance with the protocol, good clinical practice (GCP), and the applicable regulatory requirements.

Both Clickotine and QuitGuide were developed to follow US Clinical Practice Guidelines for smoking cessation interventions. Use of either app may produce risks caused by the nicotine withdrawal associated with any attempt to quit smoking, including irritability and insomnia. Both QuitGuide and Clickotine are commercially available apps. Neither includes manufacturer's safety warnings nor involves any medical recommendations regarding use of prescription or over the counter quit aids.

Preliminary data related to the safety of Clickotine were obtained in a clinical trial of 416 smokers. Negative health events were ascertained via spontaneous report by users in-app, and via proactive ascertainment by a focused question in the Week 8 questionnaire: "At any point during the study did you experience a negative health event?" All negative health events reported were sent to the Medical Monitor for evaluation. The medical monitor assessed each event, and, when needed in order to comprehensively assess and document reported events, requested additional information via study team members in contact with the participant. All events judged clinically significant by the medical monitor were considered adverse events (AEs). The medical monitor also made a determination of relatedness to Clickotine (possibly related, not related) based on all available information and clinical judgment. Four negative health events were reported spontaneously, and an additional 32 were reported in response to the focused safety question in the 8-week questionnaire. Of these 36 negative health events, 19 were considered clinically significant and documented as AEs. Of the 19 AEs, 2 were considered possibly related to Clickotine use in the judgment of the Medical Monitor (nightmare, depressed mood). The most common AE was fatigue (reported in 3 participants), mood change was reported in 2 participants, and no additional AE occurred in more than one participant.

No manufacturer safety warnings are associated with the iCO Smokerlyzer device and the minimal risk associated with its use is related to the potential loss of privacy stemming from accidental disclosure of the data produced by the reading of carbon monoxide.

Collection, reporting and management of AEs and SAEs:

All Adverse Events that occur during study participation will be solicited from study participants in both groups via an email-based system for reporting AE/SAEs. Participants are made aware of the email system during the informed consent and study enrollment process. Reports are reviewed by the research coordinator and the PI within 24 hours of the report, and conveyed to the Medical Monitor (MM) for review and follow-up if appropriate. A Medical Monitoring form is completed for each AE reported to the MM, to include: a description of the event; onset/offset dates; treatment required and/or condition resolution; designation as AE/SAE; and judgment of association with study intervention. Expedited review will occur for all events reported by study participants that meet the FDA definition of Serious Adverse Events (SAEs) – i.e., any fatal event, immediately life-threatening event, permanently or substantially disabling event, event requiring or prolonging inpatient hospitalization, or any congenital anomaly. This also includes any event that a study investigator judges to impose a significant hazard, contraindication, side effect, or precaution. Reporting to NIH will be done according to NIH regulations governing SAE reporting: the PI will contact NIDA within 72 hours after the detection of a SAE. Reporting of Suspected Unexpected Serious Adverse Reactions (SUSARs; defined by WIRB as "unanticipated adverse device effects") to Western IRB will be done within 5 days of the SUSAR report in accordance with WIRB policy.

Trial Efficacy

No interim analyses of efficacy data will be conducted as this is a brief, feasibility study. Efficacy analyses will be conducted after data collection only.

DSM Plan Administration

The Study PI ([name]) will have the primary responsibility for monitoring the trial. [name] will meet monthly with the research coordinator to monitor data entry and completeness, as well as to ensure appropriate safety data monitoring and reporting. [name] will regularly monitor potential risks and procedures for protecting against risks and will monitor the progress of the study, including periodic assessments of data quality and timeliness, participant recruitment, accrual and retention, participant risk, and other factors that can affect study outcome. The PI will also consider factors external to the study, such as scientific or therapeutic developments that may have an impact on the safety of the participants or the ethics of the study.

Data and Safety Monitoring Board: a Data and Safety Monitoring Board (DSMB) was not deemed necessary and will not be created for this trial.

Frequency of Data and Safety Monitoring: [name] will meet monthly with the research coordinator to monitor data entry and completeness, as well as to ensure appropriate safety data monitoring and reporting.

Monitoring of Safety Data: For the purpose of monitoring the safety of the study, the PI will review not only adverse events (AEs) and serious adverse events (SAEs), but other data that may reflect differences in safety between treatment groups. This includes treatment retention rates, reasons for drop-out, physical and emotional discomforts associated with being in the study, and side effects. In the event that differences between groups are apparent, the PI will consult with NIDA to determine further evaluation of safety.

Serious Adverse Events: Expedited review will occur for all events meeting the FDA definition of Serious Adverse Events (SAEs) – i.e., any fatal event, immediately life-threatening event, permanently or substantially disabling event, event requiring or prolonging inpatient hospitalization, or any congenital anomaly. This also includes any event that a study investigator judges to impose a significant hazard, contraindication, side effect, or precaution. For purposes of this study, all SAEs will be required to be reported to the IRB and NIDA, regardless of any judgment of their relatedness to the study intervention. All relevant information will be reported including information about the event and its outcome, the subject's medical history and current conditions, and any relevant laboratory data. Information will be reviewed and a determination made of whether there was any possible relevance to the study intervention. Reporting to Western IRB and NIDA will be done within 72 hours of detection of the SAE.

Non-Serious Adverse Events: In monthly data review meetings, the PI will review summaries of the numbers and rates of adverse events by treatment group compiled by the research coordinator. These reports will include types of events, severity, and outcome if available. At the same intervals, the PI will also receive summary reports of treatment retention and reasons for drop-out, by treatment arm. In the event that differences in AE or retention rates between groups are apparent, the PI will consult with NIDA to determine further evaluation of safety.

Study Stopping Rules: If at any time during the course of the study, the PI or NIDA judges that risk to subjects outweighs the potential benefits, either shall have the discretion and responsibility to recommend that the study be terminated.

Monitoring of Data Quality: In the monthly Data and Safety monitoring meeting the PI will receive a report on data quality and completeness. At a minimum, this will include an overview of the progress of patient intake and retention; summary reports describing patient compliance with surveys and CO monitoring as described in the protocol; and a summary of the completeness and quality of key data elements needed to characterize patients and their primary and secondary outcomes.

Data and Safety Monitoring Reports: After the monthly meetings, the PI and research coordinator will prepare a summary report of their findings regarding safety and data quality based on data received to that point in the study. This report will include a brief description of the trial; baseline sample characteristics as available; summary of all safety findings; as well as an assessment of protocol compliance and data quality.

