**Smoking:** Results were analyzed in the intent-to-treat (ITT) population standard for clinical trials and recommended for smoking research (West, Hajek, Stead, & Stapleton, 2005), such that enrolled subjects who did not complete the 8-week survey were assumed to still be smoking. Since this methodology may bias the reported effects of interventions (Blankers et al., 2016), the data were also analyzed only in the population who completed the survey (case completer). In the ITT sample (n=416), at the end of the 8-week study period, 45.2% of subjects reported achieving 7-day abstinence and 26.2% of subjects achieved 30-day abstinence. Among the 365 case completers, 51.5% of subjects reported achieving 7-day abstinence and 29.9% of subjects achieved 30-day abstinence.

**Summary:** This single-arm clinical trial demonstrated Click's ability to conduct research using the methodology that will be used in the proposed two-arm RCT, generated the pilot data for Clickotine's impressive efficacy that were used to derive the power analysis, and provided the estimate of the enrollment yield and retention rate used to budget for recruitment to reach the target n of subjects.

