**Exhaled CO assessment:**

- Participants will submit exhaled CO assessment via their iCO Smokerlyzer
- Participants will have the opportunity to conduct the CO assessment via live video monitoring to confirm identity
- The assessment will be used to compare CO measurement with self-report data

At Day 56, if the participant has already completed the Outcome Survey and submitted their exhaled CO assessment, they will receive an EOS: Thank you letter (*Appendix 15.13.*) via SMS and email. If the participant has not completed the Survey or CO assessment the study coordinator will then intervene as per the protocol outline follow-up attempts procedure (*Section 6.3*).

On Day 59, the trial period ends, and the Outcome Survey link will expire at the end of the day. Participants who have not completed the Survey or CO assessment after the follow-up attempts procedure will be considered as a Lost to Follow-up participant.

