## **7.11 Withdrawal Criteria/ Participant Withdrawal**

Participants will be instructed that they are free to withdraw from the study at any time without penalty or implications for any healthcare they receive. Participants who terminate the study early for any reason will be considered withdrawn.

Participants who were randomly assigned and withdraw from the study will not be replaced, regardless of the reason for withdrawal. If a participant does not complete a scheduled or required assessment or survey, every effort should be made to contact the participant. In any circumstance, every effort should be made to document participant outcome, if possible.

Reasonable efforts will be made by the research coordinator to retain participants in the study and to complete study assessments within protocol specified timeline. In the event a participant misses a required activity or assessment, follow-up efforts will include outreach via SMS, email, and phone-per the protocol follow-up procedure (Section 6.3).

If the participant withdraws from the study, and also withdraws consent for disclosure of future information, no further evaluations should be performed, and no additional data should be

collected. The sponsor may retain and continue to use any data collected before such withdrawal of consent. Subjects who do not complete the final outcome survey at 8 weeks will be considered Lost to Follow-Up and will not receive any compensation for participation. Subjects will receive payment for all completed study assessments after submission of the outcome survey at week 8.

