**1. Have you smoked (even a puff) in the last 30 days?**

- YES
- NO

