**3. If YES, have you smoked (even a puff) in the last 7 days?**

- YES
- NO

*~~ If the answer is “YES” to any of the questions 1-3, users will be prompted to Fagerstrom Test (Questions 4-9) for Nicotine Dependence*

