**18. Please answer these smoking-related questions to the best of your ability**

|  | Not at all | Very Little | A Little | Moderately | A lot | Quite a lot | Extremely |
|--|-------------------|--------------------|-----------------|-------------------|--------------|--------------------|------------------|
| Do you find cigarettes satisfying?     | 1                 | 2                  | 3               | 4                 | 5            | 6                  | 7                |
| Do cigarettes taste good to you?       | 1                 | 2                  | 3               | 4                 | 5            | 6                  | 7                |
| Do you enjoy smoking cigarettes?       | 1                 | 2                  | 3               | 4                 | 5            | 6                  | 7                |
|  | Not at all | Very Little | A Little | Moderately | A lot | Quite a lot | Extremely |
| Does smoking cigarettes calm you down? | 1                 | 2                  | 3               | 4                 | 5            | 6                  | 7                |

|   |   |   |   |   |   |   |   |
|---|---|---|---|---|---|---|---|
| Does smoking cigarettes make you feel more awake?     | 1 | 2 | 3 | 4 | 5 | 6 | 7 |
| Does smoking cigarettes make you feel more irritable? | 1 | 2 | 3 | 4 | 5 | 6 | 7 |
| Does smoking cigarettes help you concentrate?         | 1 | 2 | 3 | 4 | 5 | 6 | 7 |
| Does smoking cigarettes reduce your hunger for food?  | 1 | 2 | 3 | 4 | 5 | 6 | 7 |

|  | Not at all | Very Little | A Little | Moderately | A lot | Quite a lot | Extremely |
|--|------------|-------------|----------|------------|-------|-------------|-----------|
| Does smoking cigarettes make you less dizzy? | 1          | 2           | 3        | 4          | 5     | 6           | 7         |
| Does smoking cigarettes make you nauseous?   | 1          | 2           | 3        | 4          | 5     | 6           | 7         |

|  | Not at all | Very Little | A Little | Moderately | A lot | Quite a lot | Extremely |
|--|------------|-------------|----------|------------|-------|-------------|-----------|
| Do you enjoy the sensation in your throat and chest when you smoke cigarettes? | 1          | 2           | 3        | 4          | 5     | 6           | 7         |

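### An answer to the primary question in an unfinished outcome survey has no stated status and would most likely be scored as smoking; save questions 1–3 separately and define non-response

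*SAP*

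**What the plan says.** The primary endpoint is self-reported 30-day abstinence on the outcome survey (section 10.3 in both documents). It is question 1 of Appendix 15.4: "Have you smoked (even a puff) in the last 30 days". The survey is numbered to 24 and ends with a single Finish step.

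Four statements bear on what happens to a survey that is started but not finished:

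- SAP, Quality Assurance: for the web-based surveys used for primary data collection, "forms can not be submitted unless complete and incomplete fields can be highlighted for participants".
- SAP, Data Acquisition: the coordinator enters survey data within 72 hours of survey completion. Nothing is said about answers that were never submitted.
- Protocol 7.11: "Subjects who do not complete the final outcome survey at 8 weeks will be considered Lost to Follow-Up". Sections 7.10 and 8.2 apply the same status to anyone missing the survey or the CO assessment. On the last day, Day 59, "the Outcome Survey link will expire at the end of the day" (7.10).
- SAP, Data Analysis Plan: the ITT analysis is done "with non-response imputed as continued smoking". This rule is absent from section 10 of the protocol and from sections 10.1–10.5 of the SAP.

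The plan also works to obtain the survey. The link is open from Day 53 to Day 59 (7.10). SMS and email reminders go out on Days 56 and 57, with a phone call on Day 58 (6.3). Completing the survey earns $50 (8.2), and those who do not complete it are paid nothing (7.11).

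**The concern.** Read together, these statements make submission of the whole form the condition for the primary answer to count. A participant who has told the trial they are abstinent, but has not reached Finish by the end of Day 59, has answered the primary question yet would probably be handled as if they had not.

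The error runs one way. Someone who answers Yes and stops is scored as smoking with or without the answer. Only someone who answers No can be misclassified, and then always as a failure. If break-off is equal in the two arms, both quit rates and the absolute difference shrink. If it is unequal, the difference is distorted in whichever direction the imbalance runs. This loss could be avoided, unlike that from participants who never open the survey.

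**Working it through.** **1. Length of the form for an abstainer.** Questions 2–9 are skipped after a No to question 1: questions 2 and 3 appear only after a Yes, and a Yes "to any of the questions 1-3, users will be prompted to Fagerstrom Test" (questions 4–9). A No to question 10 skips 11–16. What remains is Q1 (1), Q10 (1), Q17 (3), Q18 (12), Q19 (1), Q20 (1), Q21 (7), Q22 (3) and Q23 (1). The total is 30 items, so 29 follow question 1, or 30 if the video invitation (Q24) is shown. Taking all of them as mandatory is a reading of the Quality Assurance sentence; the SAP does not list the mandatory fields.

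**2. The plan's own figure.** Section 10.5 gives p1 = 0.262, p2 = 0.083, two-sided α = 0.05 and 78 per arm for 85% power. With pooled variance under the null and mean rate 0.1725:

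- √(2 × 0.1725 × 0.8275) = 0.5343
- √(0.262 × 0.738 + 0.083 × 0.917) = 0.5191
- z = (0.179 × √78 − 1.960 × 0.5343) / 0.5191 = 1.028, so power is 84.8%
- required n = [(1.960 × 0.5343 + 1.036 × 0.5191) / 0.179]² = 78.4 per arm

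The stated sample size is reproduced and is not in question.

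**3. Participants at stake.** Expected quitters are 78 × 0.262 = 20.4 (CKT) and 78 × 0.083 = 6.5 (QG). Each quitter lost moves an arm's rate by 1/78 = 1.28 points.

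**4. Sensitivity.** Let f be the share of would-be reported quitters who answer No to question 1 and never submit. The documents give no value for f; 3–10% is assumed for illustration. An affected arm's rate becomes p × (1 − f). CKT quitters lost are 20.4 × 0.03 = 0.6 to 20.4 × 0.10 = 2.0; QG quitters lost are 6.5 × 0.03 = 0.2 to 6.5 × 0.10 = 0.6. The power formula of step 2, with the reduced rates, gives:

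| f | Both arms: difference, power | CKT only: difference, power | QG only: difference, power |
|---|---|---|---|
| 0 | 17.9 points, 84.8% | 17.9 points, 84.8% | 17.9 points, 84.8% |
| 3% | 17.4, 83.4% | 17.1, 82.1% | 18.1, 86.0% |
| 5% | 17.0, 82.5% | 16.6, 80.1% | 18.3, 86.8% |
| 10% | 16.1, 79.9% | 15.3, 74.6% | 18.7, 88.6% |

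In the last column the gain in power is spurious, because the difference is overstated. With no true difference and a common rate of 17.25%, break-off in one arm only raises the two-sided type I error from 5% to 5.2% at f = 5% and 6.0% at f = 10%.

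**5. What the planning rate already contains.** Protocol 1.3 says of the pilot that "enrolled subjects who did not complete the 8-week survey were assumed to still be smoking", and the 26.2% is the rate on that basis (n = 416, of whom 365 completed the survey). Any comparable break-off in the pilot is therefore already inside the 26.2%. Only break-off beyond the pilot's would lower CKT below plan, so the power losses in the table are upper bounds.

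**The case against.** The strongest objection is that no passage says what happens to a participant who answers question 1 and stops. The SAP does not define non-response, does not say which fields are mandatory, and does not say whether the platform keeps unsubmitted answers. Lost to follow-up is an operational status, not an analysis rule, and Protocol 7.11 asks for every effort to document the outcome. This stands. A reader might infer that the plan contains a rule discarding an answered question 1; it does not. What it has is an undefined term combined with a complete-to-submit form, and the scoring as smoking is the most likely consequence.

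Second, the complete-to-submit sentence sits in the monitoring-plan part of the SAP, which differs from the protocol elsewhere (Android 4.1 against 7; a CO cut-off below 8 ppm against below 7 ppm). Protocol 11.1 carries over the data-acquisition text but not that sentence, so it may no longer describe the survey. The doubt is fair, but the only statement of the smoking imputation is in the same part, so the question of what counts as non-response stays open.

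Third, stopping is not final. Reminders, the call and the payment bring people back. They lower the break-off rate, but they do not preserve an answer already given.

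Fourth, the size is small and assumed. All-cause non-completion in the pilot was 51/416 = 12.3%, so 10% break-off after question 1 would be a high figure. At an equal 10% the unadjusted odds ratio moves only from 3.92 to 3.82. This also stands.

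Two further readings are tempting. One is that dissatisfaction with the app, asked about at question 17, would make break-off differ by arm; nothing in the documents supports that or its direction. The other is that question 18 (for example "Do you find cigarettes satisfying") needs a not-applicable option for people who have quit. Each item already offers a lowest response of not at all, and the same items are asked at baseline (Appendix 15.3, question 30), so changing the scale would disturb that comparison.

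**Conclusion.** The point holds as a cheap improvement in how the primary outcome is captured and defined. An abstainer whose survey is unfinished when the link closes would most likely be scored as smoking despite having answered the primary question.

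On an assumed 3–10% break-off among quitters, about 0.6–2.0 of some 20 CKT quitters would be lost. If the arms are equally affected, power falls from 84.8% to between 83.4% and 79.9% at most. Imbalance would bias the comparison in either direction. A reader might take these figures as a forecast that the planned 17.9-point difference will shrink. The documents do not support that: they give no break-off rate, and the planning rate already absorbs break-off at the pilot's level.

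The conclusion rests on three assumptions: that the complete-to-submit rule applied to the outcome survey, that unsubmitted answers are not retrieved, and that survey non-completion is what the SAP means by non-response.

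**What to change.** - Put questions 1–3 on their own first page and save them when that page is submitted. Keep the full-completion requirement for the remaining pages and for the $50 payment, so that the incentive to finish is unchanged.
- State in section 10.3 and in the Data Analysis Plan that non-response means no saved answer to question 1, whether or not the rest of the survey or the CO reading is completed, and that only non-response so defined is imputed as smoking. This puts the imputation rule into section 10. It also removes the doubt left by sections 7.10 and 8.2, under which a participant with a submitted survey but no CO reading is lost to follow-up.
- Leave question 18 as it is.

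The cost is a survey-platform setting and a sentence in each of two places. The downside is that some records will have a primary outcome but lack secondary items (such as quit-aid use at question 10) or the adverse-event item (question 23). Under the present arrangement those records would most likely contribute nothing from the outcome survey.
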